3.6 Post Study Drug Study Follow up

In this study, overall survival is a key endpoint of the study. Post study follow-up is of critical importance and is essential to preserving subject safety and the integrity of the study. Subjects who discontinue study drug must continue to be followed for collection of outcome and/or survival follow-up data as required and in line with [Table 5.1-3](#) until death, withdrawal of consent, lost to follow-up or the conclusion of the study.

In addition, subjects who discontinue study therapy by proceeding to allogeneic SCT or ASCT will require tumor assessment (CR or non-CR) by the investigators according to the Lugano Classification 2014 (DLBCL/PTCL) and consensus Global Response Score (CTCL) on day 100, at 6 months, 1 year and every year thereafter from the date of stem cell infusion until the first non-CR after SCT is documented. For the subjects who discontinue study therapy by proceeding to allogeneic SCT, documentation of acute and chronic GVHD will be simultaneously collected see [Appendix 5](#) for more details.

Subjects who discontinue study drug may continue to be followed. BMS may request that survival data be collected on all *treated* subjects outside of the 3 month specified visit schedule. At the time of this request, each subject will be contacted to determine their survival status unless the subject has withdrawn consent for all contact.

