GVHD Assessments			Only for subjects who proceed to allogeneic SCT. To be assessed on Day 100, at 6 months, at 1 year and every 1 year thereafter from the date of stem cell infusion until the first non-CR after SCT is documented. Refer to Appendix 5 for further details.
Subsequent Anticancer Therapy	X	X	
Other Primary Malignancies	X	X	
Biomarker Assessments			
Serum, Tumor Biopsy, Bone Marrow Aspirate/biopsy	See Note		Optional biomarker samples collected at time of progression. See Table 5.6-1 for biomarker sampling details
Pharmacokinetic/Immunogenicity Assessments			
PK and Immunogenicity samples	X		See Table 5.5.1-1 for PK and immunogenicity sampling details
Outcomes Research Assessments			
EQ-5D 3L Questionnaire	X	X	EQ-5D-3L questionnaires administered during survival follow-up will be completed in clinic or via phone contact. Refer to section 5.7 for more information. To be completed only for subjects enrolled in the Expansion Phase (Cohort B).

Table 5.1-3: Follow-up Assessments (CA209436)			
Follow-up Assessments (CA209436)			
Procedure	Follow Up, Visits 1 and 2^a (X01 & X02)	Survival Follow-Up Visits^b	Notes
Subject Status			
Survival Status	X	X	Survival follow-up visits are expected to occur every 3 months after X02; may be accomplished by visit, phone contact or email, to update survival information and assess subsequent anti-cancer therapy. BMS may request that survival data be collected on all treated subjects outside of the 3 month specified window. At the time of this request, each subject will be contacted to determine their survival status unless the subject has withdrawn consent for all contact.

^a Follow-up visit 1 (X01) = 35 days from the last dose +/- 7 days. Follow-up visit 2 (X02) = 80 days (+/- 7 days) from follow-up visit X01.

^b Survival Follow-up visits to occur every 3 months from X02. BMS may request that survival data be collected on all treated subjects outside of the 3 month specified window. At the time of this request, each subject will be contacted to determine their survival status unless the subject has withdrawn consent for all contact.

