Thyroid function testing is to be done at every other cycle (approximately every 6 weeks, unless treatment delays are observed) for subjects receiving study drug. At baseline TSH, Free T3 and Free T4 will be performed within 14 days of first dose. During treatment TSH will be done (with reflexive Free T4 and Free T3 if TSH results are abnormal) within 72 hours prior to dosing.

On treatment local laboratory assessments should be done within 72 hours prior to dosing; and will include CBC with differential, BUN or serum urea level, serum creatinine, sodium, potassium, calcium, magnesium, chloride, amylase, lipase, glucose, AST, ALT, total bilirubin, alkaline phosphatase and LDH.

Local laboratory assessments are to be performed for the Follow-up X01 visit and include CBC with differential, uric acid, serum urea level, uric acid, albumin, creatinine, sodium, potassium, calcium, magnesium, chloride, glucose, AST, ALT, total bilirubin, alkaline phosphatase, LDH, TSH (reflex to free T3, free T4 for abnormal TSH result). This panel should be repeated at Follow-up visit X02 if Follow-up visit X01 results were abnormal.

For subjects who discontinue study therapy by proceeding to allogeneic SCT, documentation of acute and chronic GVHD will be captured on **Day 100, at 6 months, 1 year and every year thereafter from the date of stem cell infusion** until the first non-CR after SCT is documented.

Subjects will be evaluated for safety if they have received any study drug. Toxicity assessments will be continuous during the treatment phase. During the Follow-Up Phase at Visits X01 and X02, toxicity assessments should be done in person. Follow-up visit 1 (X01) is to occur 35 days from the last dose +/- 7 days. Follow-up visit 2 (X02) is to occur 80 days (+/- 7 days) from follow-up visit X01. Once subjects reach the survival follow-up phase, either in-person visits or documented telephone calls/email correspondence to assess the subject's status are acceptable. Survival visits should occur every 3 months. BMS may request that survival data be collected on all treated

subjects outside of the 3 month specified window. At the time of this request, each subject will be contacted to determine their survival status unless the subject has withdrawn consent for all contact.

Adverse events and laboratory values will be graded according to the NCI-CTCAE version 4.03.

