6.1.1 Serious Adverse Event Collection and Reporting

Sections 5.6.1 and 5.6.2 in the Investigator Brochure (IB) represent the Reference Safety Information to determine expectedness of serious adverse events for expedited reporting. Following the subject's written consent to participate in the study, all SAEs, whether related or not related to study drug, must be collected, including those thought to be associated with protocol-specified procedures. All SAEs must be collected that occur during the screening period and within 100 days of the last dose of *study drug*. If applicable, SAEs must be collected that relate to any later protocol-specified procedure (eg, a follow-up skin biopsy).

The investigator must report any SAE that occurs after these time periods and that is believed to be related to study drug or protocol-specified procedure.

An SAE report must be completed for any event where doubt exists regarding its seriousness.

If the investigator believes that an SAE is not related to study drug, but is potentially related to the conditions of the study (such as withdrawal of previous therapy or a complication of a study procedure), the relationship must be specified in the narrative section of the SAE Report Form.

SAEs, whether related or not related to study drug, and pregnancies must be reported to BMS (or designee) within 24 hours of awareness of the event. SAEs must be recorded on the SAE Report Form; pregnancies on a Pregnancy Surveillance Form (electronic or paper forms). The preferred method for SAE data reporting collection is through the eCRF. The paper SAE/pregnancy surveillance forms are only intended as a back-up option when the eCRF system is not functioning. In this case, the paper forms are to be transmitted via email or confirmed facsimile (fax) transmission to:

SAE Email Address: Refer to Contact Information list.

SAE Facsimile Number: Refer to Contact Information list.

For studies capturing SAEs through electronic data capture (EDC), electronic submission is the required method for reporting. In the event the electronic system is unavailable for transmission, paper forms must be used and submitted immediately. When paper forms are used, the original paper forms are to remain on site.

SAE Telephone Contact (required for SAE and pregnancy reporting): Refer to Contact Information list.

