7.6.9.1 Transplant

Number and percentage of subjects by response category (CR, non-CR, unable to determine) will be provided at the time of transplant and at the 100 days, 6 months and 1 year timepoints after transplant for subjects undergoing subsequent allogeneic SCT and autologous SCT separately. Denominators will be based on subjects with assessment available by timepoint.

For subjects undergoing allogeneic SCT, number and percentage of subjects with GVHD will be provided at the 100 days, 6 months and 1 year timepoints: chronic limited, chronic extensive, acute (grade I, II, III, IV, unknown). Denominators will be based on subjects undergoing allogeneic SCT with assessment available by timepoint.

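### GVHD percentages after allogeneic transplant leave out subjects who die before Day 100 and, at later visits, survivors whose documentation stopped at non-CR

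*SAP*

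**What the plan says.** SAP 7.6.9.1 (Transplant), which sits under Adverse Events of Special Interest, says that "number and percentage of subjects with GVHD will be provided at the 100 days, 6 months and 1 year timepoints", split into chronic limited, chronic extensive and acute grades I to IV or unknown. The denominator rule is "Denominators will be based on subjects undergoing allogeneic SCT with assessment available by timepoint". No category is given for death before a visit, and no worst-grade or ever-GVHD summary is planned.

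The protocol ties GVHD collection to the post-transplant response visits. Section 3.6 says that for allogeneic recipients "documentation of acute and chronic GVHD will be simultaneously collected" with the CR or non-CR assessment. The schedule is Day 100, 6 months, 1 year and then yearly. The GVHD row of Table 5.1-3 runs that schedule "from the date of stem cell infusion until the first non-CR after SCT is documented", and section 5.3 repeats both the schedule and the stop.

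There are other recording routes. Section 6.1.1 says "All SAEs must be collected that occur during the screening period and within 100 days of the last dose of" study drug, and section 6.2.1 gives nonserious events the same 100-day limit. Later SAEs must be reported only if believed related to study drug or to a protocol-specified procedure. Section 3.1 follows all treated subjects for survival until death or loss to follow-up.

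**The concern.** An available-assessment denominator is reasonable when missing a visit has nothing to do with the outcome. Here it can. Acute GVHD can occur and prove fatal before Day 100, and the first scheduled documentation is at Day 100. A subject who dies in that interval has no scheduled assessment, so the stated rule drops the subject from every row of the table. What remains is a percentage among subjects who lived to be assessed, shown without the number transplanted beside it.

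A second and distinct loss follows from the stopping rule. Ending collection at the first non-CR suits a response endpoint, but GVHD is a safety outcome that can still develop or worsen in a subject who is not in CR. The documents give no reason why its documentation should end there.

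Prior allogeneic transplant is an exclusion criterion (Protocol 3.3.2), so the table describes subjects who go from the study combination to a transplant. It is the only GVHD summary set out in the two documents.

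**Working it through.** **Inputs.** The denominator rule and timepoints come from SAP 7.6.9.1. The schedule and stop come from Protocol 3.6, 5.3 and Table 5.1-3. The 100-day safety window comes from Protocol 6.1.1 and 6.2.1. Neither document gives a transplant count, a GVHD rate or an early death rate, so there is no figure to reproduce. All counts below are assumptions.

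**Loss 1: deaths before Day 100.** Let n be the number transplanted, g those with GVHD by Day 100, d the deaths before Day 100, and dg the deaths among those with GVHD.

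- Reported under the SAP rule, if every survivor is assessed and the form captures GVHD since infusion: (g − dg)/(n − d).
- All transplanted: g/n.
- The reported value is lower when n(g − dg) < g(n − d), that is, when dg/d > g/n.

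The direction therefore depends on who dies early. With n = 12, g = 3 and d = 2, the true value is 3/12 = 25%:

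| dg | Reported | Direction |
|---|---|---|
| 2 | 1/10 = 10% | understated |
| 1 | 2/10 = 20% | understated |
| 0 | 3/10 = 30% | overstated |

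The next table varies the size, taking every early death to be a GVHD death (f of them, with s cases among assessed survivors). The comparison is s/(N − f) against (s + f)/N:

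| N | f | s | Reported | All transplanted |
|---|---|---|---|---|
| 5 | 1 | 1 | 1/4 = 25.0% | 2/5 = 40.0% |
| 5 | 3 | 0 | 0/2 = 0.0% | 3/5 = 60.0% |
| 10 | 1 | 2 | 2/9 = 22.2% | 3/10 = 30.0% |
| 10 | 2 | 3 | 3/8 = 37.5% | 5/10 = 50.0% |
| 15 | 1 | 6 | 6/14 = 42.9% | 7/15 = 46.7% |
| 15 | 3 | 2 | 2/12 = 16.7% | 5/15 = 33.3% |

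Across N of 5, 10 and 15 with 1 to 3 early GVHD deaths, the shortfall ran from about 4 to 60 points. The 60-point case is the extreme N = 5, f = 3. With no early death the two percentages agree at Day 100. Every row falls short because this table contains only GVHD deaths; it says nothing about other causes.

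**Loss 2: stop at non-CR.** Take N = 10 with 2 early deaths, leaving 8 assessed at Day 100. If 3 of the 8 are non-CR at that visit, collection ends for them and the 6-month denominator is 10 − 2 − 3 = 5 of 10 transplanted. The Day 100 row is unaffected by these 3. The 6-month and 1-year rows, where chronic GVHD would be read, no longer contain them.

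**Does routine event reporting fill the gap?** Its clock starts at the last dose, whereas the GVHD visit is timed from infusion. If infusion is k days after the last dose, routine collection ends on post-transplant day 100 − k. For an assumed k of 30 to 60 days, that is day 70 to day 40. The second follow-up visit falls 35 + 80 = 115 days after the last dose, or post-transplant day 115 − k, so it too precedes Day 100 once k exceeds 15 (ignoring visit windows). Coverage is partial, and neither document says that SAE reports or causes of death feed the GVHD table.

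**The case against.** The strongest reply is that little is lost to the trial as a whole. Deaths are a primary safety endpoint with their own summary, every treated subject is followed for survival, and a late SAE thought to be related to study drug must still be reported. SAP sections on deaths, SAEs and events of special interest defer to a Core Safety SAP that is not among the documents, so a further GVHD summary there cannot be ruled out. The GVHD form is not shown either. It may record the worst grade since infusion, and it might be completed after a death. The table is descriptive, GVHD is not a stated objective or listed endpoint, and Protocol 1.5 says most such patients are ineligible for allogeneic transplant, so numbers may be small.

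Most of this stands, and it limits the point to the GVHD percentages. It does not rescue the denominator rule, which is explicit and has no provision for subjects who die before a visit. Small numbers make each omitted case count for more.

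A reader might infer four stronger things that the documents do not support:

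- That the table is always biased towards safety. The direction depends on dg/d against g/n, and the 30% case above runs the other way.
- That the non-CR stop is what removes fatal early GVHD. It is not; it affects survivors at later visits.
- That fatal GVHD vanishes from the trial. The death remains in overall survival and death reporting, and a GVHD death after the Day 100 visit is still counted at Day 100.
- That GVHD after checkpoint blockade is declared a key safety question. Neither document says so.

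**Conclusion.** The point holds within the GVHD table. Subjects who die before Day 100 are absent from numerator and denominator at all three timepoints. Separately, survivors whose first non-CR has been documented are missing from the 6-month and 1-year rows. The error is an understatement when GVHD is more common among early deaths than among all transplanted subjects, and may be an overstatement otherwise. Its size cannot be computed from the documents; on assumed counts of 12 transplanted and 3 cases, the report ranges from 10% to 30% against 25%. This rests on GVHD being captured only at the scheduled visits, and on no other GVHD summary existing in the Core Safety SAP. It does not touch the primary analysis and is best treated as a cheap improvement.

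**What to change.** In SAP 7.6.9.1:

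- Use all subjects who received allogeneic SCT as the denominator at every timepoint.
- Report the worst acute GVHD grade and any chronic GVHD recorded since infusion, from any source: GVHD form, SAE report or cause of death.
- At each timepoint add a row for subjects who died before assessment, split by cause (GVHD or other), and a row for subjects not assessed because collection stopped at non-CR.

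With a fixed denominator, an unassessed subject with no GVHD record counts as no recorded case. The percentage is then a minimum, and the added rows show how far it could rise. Cumulative incidence with death without GVHD as a competing event is optional, if there are enough transplants to support it.

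These are wording and table-shell changes that use data already due to be collected, so the cost is small.

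The sponsor should also consider separating GVHD documentation from the non-CR stop in Protocol 3.6, 5.3 and Table 5.1-3. This costs more. It is a protocol amendment needing ethics approval under section 9.1.1, and it adds data collection for non-CR subjects, whose scheduled post-transplant assessments currently end and whose remaining follow-up may be by telephone or email. If it is not adopted, the row for stopped collection at least makes the gap visible.

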7.6.10 Clinical Laboratory Evaluations

The analysis population for each laboratory test is restricted to treated subjects who underwent that laboratory test.

7.6.10.1 Hematology

See Core Safety SAP

7.6.10.2 Serum Chemistry

See Core Safety SAP

7.6.11 Vital Signs and Pulse Oximetry

See Core Safety SAP

7.6.13 Pregnancy

By-subject listing of pregnancy tests results will be provided

7.6.14 Clinical Safety Program (CSP)

See Core Safety SAP

7.8.2.2 Evaluation of associations between CD30 at baseline and efficacy measures

Analyses for ORR (BOR):

- Box plots of CD30 expression versus BOR will be generated for all CD30 evaluable subjects
- A logistic regression model of ORR (responder, non-responder) will be produced with baseline CD30 expression as continuous covariate.

Analyses of PFS and OS:

- A Cox proportional hazards model of OS will be produced with Baseline CD30 expression as continuous variable.
- A Cox proportional hazards model of PFS will be produced with Baseline CD30 expression as continuous variable.

7.10 Interim Analyses

No formal interim analysis is planned. Interim analyses may be conducted if it is necessary in order to make decisions regarding further development. Summaries and listings of efficacy and safety will be provided. Interim analyses will not impact the study conduct and the trial will continue as planned.

8 CONVENTIONS

The following conventions may be used for imputing partial dates for analyses requiring dates:

- For missing and partial adverse event onset dates, imputation will be performed using the Adverse Event Domain Requirements Specification⁹.
- Missing and partial Non-Study Medication Domain dates will be imputed using the derivation algorithm described in 4.3.3 of BMS Non-Study Medication Domain Requirements Specification¹⁰.

For death dates, the following conventions will be used for imputing partial dates:

- If only the day of the month is missing, the 1st of the month will be used to replace the missing day. The imputed date will be compared to the last known date alive and the maximum will be considered as the death date.
- If the month or the year is missing, the death date will be imputed as the last known date alive. If the date is completely missing but the reason for death is present the death date will be imputed as the last known date alive

For date of progression, the following conventions will be used for imputing partial dates:

- If only the day of the month is missing, the 1st of the month will be used to replace the missing day*.
- If the day and month are missing or a date is completely missing, it will be considered as missing.
- In case of the date of death is present and complete, the imputed progression date will be compared to the date of death. The minimum of the imputed progression date and date of death will be considered as the date of progression.
- For other partial/missing dates, the following conventions may be used:
- If only the day of the month is missing, the 15th of the month will be used to replace the missing day.
- If both the day and the month are missing, "July 1" will be used to replace the missing information.
- If a date is completely missing, it will be considered as missing.

The following conversion factors will be used to convert days to months or years:

1 month = 30.4375 days and 1 year = 365.25 days.

Duration (e.g. time from first diagnosis of NSCLC to first dosing date, duration response, and time to response) will be calculated as follows:

Duration = (Last date - first date + 1)

All statistical analyses will be carried out using SAS (Statistical Analysis System software, SAS Institute, North Carolina, USA) unless otherwise noted.

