Thyroid Function Testing			See Note	TSH (reflex to free T3 and free T4 if abnormal result) to be performed at every other cycle (C3, C5, etc). Refer to section 5.3 for further details.
Pregnancy Test (WOCBP only)	X		See Note	Serum or urine within 24 hours prior to first dose and then at least once every 4 weeks regardless of dosing schedule.

Table 5.1-2: On Treatment Procedures (CA209436)				
Procedure	On treatment procedures			Notes All windows proposed are calendar days. Procedures must be done within 72h prior to dosing unless otherwise specified.
	Cycle 1 Day 1	Cycle 1 Day 8	Cycle 2 & Beyond, Day 1	
Efficacy/Biomarker Assessments				
Radiographic Tumor Assessment 
 CT chest, CT/MRI of abdomen, pelvis and any other known sites of disease (required for CTCL) FDG PET-CT (DLBCL, PTCL, PMBL & MGZL only)			See Note	Tumor assessments will occur at Week 6 and Week 12 continuing every 9 weeks (+/- 1 week) for the subsequent 4 tumor assessment timepoints, regardless of dosing schedule. After the first year, tumor assessments are to occur every 12 weeks (+/- 2 weeks) until disease progression is documented. Patients with treatment beyond progression should be evaluated at minimum every 12 weeks (see appendix 2). Radiographic evaluations in subjects with CTCL will be performed as clinically indicated by the disease stage. FDG PET-CT is the method of assessment for DLBCL, PTCL, PBML & MGZL subjects. Subjects with PET-Avid lesions at baseline should be followed with PET, subjects with non-Pet avid lesions and lesions on CT scans at baseline should be followed with CT Scans. Refer to section 5.4 for further details.
Blood tumor burden assessment (SS-CTCL only)			See Note	Only required to confirm CR in CTCL SS subjects in case blood was positive for tumor cells at screening. Refer to section 5.4.3.6 .
Modified Severity Weighted Assessment Tool			See Note	Required for subjects with Cutaneous T Cell Lymphoma as part of disease assessment. To be completed at each visit. Refer to Appendix 4 for further details.
Medical Photography			See Note	Suggested for subjects with Cutaneous T Cell Lymphomas as part of disease assessment. To be done along with the radiographic assessment timepoints. Refer to section 5.4.3.5 for further details.

Table 5.1-2: On Treatment Procedures (CA209436)				
	On treatment procedures			
Procedure	Cycle 1 Day 1	Cycle 1 Day 8	Cycle 2 & Beyond, Day 1	Notes

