4 ENDPOINTS

4.1 **Primary Endpoints**

The primary safety endpoints include DLT, incidence of deaths, adverse events, serious adverse events, adverse events leading to discontinuation, adverse events leading to dose delay, drug-related adverse events and specific laboratory abnormalities (worst grade). Toxicities will be graded using the National Cancer Institute (NCI) Common Terminology Criteria for Adverse Events (CTCAE) version 4.03.

The primary efficacy endpoint is ORR. It is defined as the number of subjects with a best overall response (BOR) of CR or PR divided by the number of treated subjects. The BOR is defined as the best response designation recorded between the date of first dose and the date of initial objectively documented progression or the date of subsequent therapy, whichever occurs first. Allogeneic SCT and ASCT will be considered as subsequent therapy. In subjects with relapsed refractory DLBCL, relapsed refractory PMBL, relapsed refractory MGZL and relapsed refractory PTCL the response (CR, PR, SD and progression) will be assessed according to Lugano Classification 2014. A CR must have been confirmed by scans, including a negative Positron Emission Tomography (PET) to be considered for CR in subjects with PTCL, PMBL, MGZL and DLBCL. For subjects with relapsed refractory CTCL, response will be assessed according to consensus Global Response Score as per the consensus statement of the International Society for Cutaneous Lymphoma.

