4.2 Secondary Endpoints

The secondary endpoints are DOR, CR rate, duration of CR, PFS and OS. All these endpoints are based on Lugano classification 2014 and Global Response score for the CTCL subjects.

DOR will be calculated from the date of initial documentation of a response (CR, or PR) to the date of first documented evidence of progressive disease (or relapse for subjects who experience CR during the study) or death due to any cause, whichever occurs first. Subjects who are progression-free and alive or have unknown status will be censored at the last tumor assessment. For subjects who received subsequent therapy prior to documented progression, duration of response will be censored on the last tumor assessment date prior to or on subsequent therapy. Allogeneic SCT and ASCT will be considered as subsequent therapy.

The CR rate is defined as the number of subjects with a BOR of CR divided by the number of treated subjects. The duration of CR will only be evaluated in subjects with BOR of CR and is defined as the time from first documentation of CR to the date of relapse or death due to any cause, whichever occurs first. Censoring will be applied as per DOR definition.

PFS is defined as the time from the date of first dose of study drug until the date of first documented evidence of progressive disease (or relapse for subjects who experience CR during the study) or death due to any cause, whichever comes first. Subjects who are progression-free and alive or have unknown status will be censored at the last tumor assessment. Subjects who did not have any on-study tumor assessments and did not die will be censored on the date of first treatment. For subjects who received subsequent therapy prior to documented progression, it will be censored on the last tumor assessment date prior to or on subsequent therapy.

Situation	Date of Progression or Censoring	Outcome
No baseline tumor assessments	First dose date	Censored
No on study tumor assessments and no death	First dose date	Censored
New anticancer treatment started without a prior reported progression or death	Date of last evaluable tumor assessment prior to or on the date of initiation of the subsequent anti-cancer therapy	Censored
Progression documented at scheduled or unscheduled visit and no new anticancer treatment started before	Date of the first documented tumor progression	Progressed
Subject progression free and no new anticancer treatment started	Date of last tumor assessment	Censored

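### The SAP's rule for a progression date with a missing day has no lower limit, so in rare records progression can precede first dose or a documented response

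*SAP*

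**What the plan says.** SAP section 8 (Conventions) handles partial death dates and partial progression dates in adjacent lists. Both begin in the same way when only the day is missing: "If only the day of the month is missing, the 1st of the month will be used to replace the missing day". They then part.

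- **Death date.** "The imputed date will be compared to the last known date alive and the maximum will be considered as the death date". This is a lower limit.
- **Progression date.** Where a complete death date exists, "The minimum of the imputed progression date and date of death will be considered as the date of progression". This is an upper limit, and no other comparison is given.

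The same section defines durations as last date minus first date plus one ("Duration = (Last date - first date + 1"). In SAP 4.2, "PFS is defined as the time from the date of first dose of study drug", and duration of response starts at the first documented CR or PR. The PFS censoring scheme (Table 4.2-1) accepts progression found at an unscheduled as well as a scheduled visit, and adds no lower limit. SAP 4.1 defines best overall response as "the best response designation recorded between the date of first dose and the date of initial objectively documented progression", or up to subsequent therapy if that comes first.

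**The concern.** A progression date ought not to precede a date on which the subject is known to have been progression-free. The plan respects the equivalent rule for deaths and omits it for progression. Two things follow.

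First, PFS or duration of response can come out at zero or below. A negative time is not admissible in a Kaplan-Meier analysis, so the subject is either dropped or repaired by a rule made up at the time. The PFS records exposed are among the earliest failures.

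Second, if the imputed date closes the best-response window, a response recorded later in that month falls outside it, and a responder can leave the primary ORR. The planned Cohort B groups have 10 to 40 subjects, so one lost responder is worth 1/10 = 10 points in MGZL, 1/20 = 5 points in CTCL and 1/40 = 2.5 points in DLBCL. (The SAP adds Cohort A subjects of the same subtype, which changes these slightly.)

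**Working it through.** The plan gives no figure to reproduce here, so the check applies its rule to dates.

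**When the rule fails.** Let the interval start (first dose for PFS, first response for duration of response) fall on day *s* of a month, and let progression fall later in the same month with the day missing. The imputed date is day 1, so

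duration = 1 − *s* + 1 = 2 − *s*.

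This is zero for *s* = 2 and negative for *s* ≥ 3. If progression falls in a later month, the imputed date is after the start and the duration is positive. The longest true interval that can fail runs from the 2nd to the 31st, which is 29 days; a negative value needs 28 days or fewer.

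**Examples** (SAP rule, SAP duration formula):

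| Start | Progression | True duration | Under the rule |
|---|---|---|---|
| First dose 10 March | March, day unknown | not known | PFS 1 − 10 + 1 = −8 |
| First dose 3 March | 24 March | 22 | PFS 1 − 3 + 1 = −1 |
| Response 3 March | 31 March | 29 | DOR 1 − 3 + 1 = −1 |
| Response 2 March | 30 March | 29 | DOR 1 − 2 + 1 = 0 |
| First dose 20 January | 3 March | 43 | PFS 41 (valid) |

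The SAP's list of durations is by way of example and does not name PFS. Without the added day, the first value would be −9, so the conclusion does not depend on it.

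**How often, given a missing day.** Taking every start date in 2017 and a fixed true gap from start to progression:

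| Gap (days) | Imputed date before start | Of which negative | Of which zero |
|---|---|---|---|
| 7 | 73.7% | 70.4% | 3.3% |
| 14 | 50.7% | 47.4% | 3.3% |
| 21 | 27.7% | 24.4% | 3.3% |
| 28 | 4.9% | 1.9% | 3.0% |
| 35 or more | 0% | 0% | 0% |

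These are conditional on the day being missing and on that gap having occurred. They are not rates in the trial.

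**Which visits can produce such gaps.** Protocol Table 5.1-2 schedules imaging at weeks 6 and 12, then every 9 weeks within one week either way. The nominal gaps are 42 and 63 days, which are safe. If the one-week window also covers weeks 6 and 12 (an assumption), the first scan is at 35 days or later, still safe for PFS, and the gap from week 7 to week 11 is 28 days, which is just short enough to affect duration of response. Otherwise the routes are an unscheduled visit or, in CTCL, the skin score, which Table 5.1-2 marks "To be completed at each visit" in 3-week cycles.

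**The case against.** The strongest reply is that this will hardly ever occur. It needs a missing day and progression in the same calendar month as first dose or first response. Protocol 5.4 requires on-study scans to be available at the sites, so most missing days can be recovered by query. That stands, and it makes the point minor.

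A reader might infer more than the documents support, in four ways.

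- *That 3-weekly CTCL skin visits put many responses at risk.* Protocol Appendix 4 asks that a CR or PR be documented for at least 4 weeks, so a response lost at 21 days may not count whatever date is imputed. Protocol 5.4 also ties the Global Response Score to tumor assessment time points. For CTCL responders only gaps of 28 to 29 days remain; early negative PFS is still possible.
- *That an imputed date before any earlier visit is an invalid time.* If that visit is neither first dose nor first response, PFS or duration of response can be too short and contradict the record, yet still be positive.
- *That a count of affected subjects can be given.* The documents state neither a rate of partial dates nor an expected number of progressions.
- *That moving dates to the 1st is itself an error.* The mean shift is 14.7 days earlier. Where the result stays valid, this shortens PFS and duration of response, a conservative convention in a single-arm trial.

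One uncertainty remains. In the SAP the progression bullet carries an asterisk with no labelled note. The bullet on the death date, just below, is its likely text, and that is an upper limit; a note lost from the text supplied cannot be excluded.

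**Conclusion.** The gap is real and minor. As written, the progression-date rule can produce zero or negative PFS or duration of response, and can place a documented response after the imputed progression. This happens only when progression shares a calendar month with first dose or first response, an interval of at most 29 days. Scheduled imaging at its nominal spacing never causes it. The expected number of records is small but cannot be calculated from the documents. The conclusion assumes that the supplied SAP text is complete at the asterisk and, for the ORR effect, that the imputed date is the one that closes the best-response window. The reason to act is that the stated rule can return impossible values, and that in an open-label study the repair is better fixed in advance than chosen record by record.

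**What to change.** Replace the progression-date bullet in SAP section 8 with:

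*If only the day is missing, the progression date is the latest of the 1st of the reported month, the first dose date, and the day after the last tumor assessment without progression that precedes the reported progression, within the reported month and not later than a complete date of death. PD back-dated to a prior IR assessment keeps that IR date.*

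The restriction to assessments before the reported progression is needed because Protocol 4.5.9 lets treatment and assessment continue after progression; without it, a later assessment could push the date forward. The last sentence is needed because Protocol Appendix 2 corrects an indeterminate response to PD at its own date when true progression follows.

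On the examples: first dose 10 March with no later assessment gives 10 March, PFS 10 − 10 + 1 = 1 day. Response on 3 March as the last progression-free assessment gives 4 March, duration of response 4 − 3 + 1 = 2 days, and the response stays inside the window. First dose 20 January with progression in March and no progression-free assessment in March stays at 41 days.

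The cost is one SAP sentence and a small change to the date derivation, with no new data. The sponsor should also confirm what the asterisk refers to.
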